6.5.4. Consumption

The total annualized rFIXFc consumption (IU/kg) will be calculated for each subject using the following formula:

$$\text{Annualized consumption} = \frac{\text{Total IU/kg of study drug received during the efficacy period}}{\text{Total number of days during the efficacy period}} \times 365.25$$

The total amount of rFIXFc received will be the sum of the nominal IU/kg administered for each injection based on the units of rFIXFc as recorded from the subject’s diary and eCRF and his most recent weight.

Total annualized rFIXFc consumption will be determined for each treatment regimen during the efficacy period (i.e., excluding surgery/rehabilitation periods [major and minor surgeries]).

For personalized prophylaxis regimen, additional injections administered will be included in the consumption calculations.

Consumption is a secondary endpoint in this study. A description of how consumption will be summarized is provided in Section 7.3.3.

6.5.5. Compliance

Prophylactic dose compliance will assess adherence to the Investigator’s recommendations for dosing. Prophylactic dose compliance will be assessed during the efficacy period.

The prophylactic dose compliance rate will be summarized for overall prophylaxis regimen for the FAS. See Section 6.5.5.2 for further details on prophylactic dose compliance.

Except for doses administered in the clinic, study treatment may be administered by a caregiver or self-administered by the older children in the study.

For the analysis of subject’s compliance with the study Protocol, data from the eCRF and eDiary will be considered.

6.5.5.1. Compliance in the Treatment of Bleeding Episodes

Bleeding episodes are defined in Section 7.1.1. All bleeding episodes during the efficacy period for which there is a date and time for both the onset of the bleed and treatment of the bleed will be evaluated for compliance. Compliance will first be determined on a per-bleed basis and then on a per-subject basis. That is, compliance for each bleeding episode will be determined and then the overall percentage of bleeding episodes for which treatment was in compliance will be determined for each subject.

The definition of compliance for the treatment of an individual bleeding episode, as specified by the Sponsor, is no more than 8 hours between the onset of the bleed and the initiation of treatment for the bleed. Thus, the compliance rate for the treatment of bleeding episodes will be

measured by determining the proportion of injections administered within a maximum of 8 hours of the initial sign of a bleed, as follows:

$$\text{Treatment of bleed compliance rate} = \frac{\text{Number of first injections to treat a bleed taken within 8 hours of the first sign of a bleed}}{\text{Total number of evaluable bleeding episodes}} \times 100$$

The following circumstances result in a bleeding episode being considered not evaluable for the determination of this compliance rate:

- the type of bleed has been classified as Unknown based on the definition of a bleeding episode (>72 hours between consecutive injections) since there is no onset time
- a missing bleed time for a spontaneous or traumatic bleed
- a bleed time that was recorded as being after the time of treatment

Bleeding episodes for which the first injection for treatment was with non-study drug will be included in the evaluation of compliance. Inclusion of bleeding episodes treated with non-study drug is discussed in Section 7.1.1.

Descriptive statistics of the per-subject compliance rate as well as a categorical summary of these data (<80%, ≥80%) will be presented for overall treatment regimen for the FAS.

6.5.5.2. Compliance of Prophylactic Injections

The compliance rate of each subject to the prescribed prophylactic dosing regimen during the efficacy period will be calculated in 2 ways, as dose compliance and as dosing interval compliance. Compliance will first be determined on a per-injection basis and then on a per-subject basis. That is, compliance for an individual dose or dosing interval will be determined and then the overall percentage of doses and dosing intervals that were in compliance will be determined for each subject.

For the purpose of evaluating compliance, the following will be considered per injection:

- the nominal dose taken compared to the nominal dose prescribed
- the actual day of treatment compared to the prescribed day of treatment

An individual dose will be considered compliant if it is within 80% to 125% of the prescribed dose. An individual dosing interval will be considered compliant if the time between two prophylactic doses is within 36 hours of the prescribed dosing interval. Prescribed dose and dosing intervals are according to the Investigator. Instructions provided to the subject by the Investigator regarding dose or dosing interval changes will be used to determine compliance as of the date the information was provided to the subject.

The actual dosing intervals will be calculated as the length of time between consecutive prophylactic doses (date/time of PR_{x+1} – date/time of PR_x). PR_{x+1} and PR_x are also discussed in Section 6.5.3. The actual time between doses will be determined in minutes and converted to days as the number of minutes divided by 1440. The prescribed dosing interval will be taken from the eCRF as recorded by the Investigator. The absolute value of the difference between the actual and prescribed dosing intervals must be ≤1.5 day (+/- 36 hours) in order to be compliant.

All prophylactic injections will be used to determine prophylactic dose compliance; only the prophylactic injections used to determine the average prophylactic dosing interval (i.e., intervals not separated by a bleeding episode or surgical/rehabilitation period), as detailed in Section 6.5.3, will be used to evaluate prophylactic interval compliance. Dose and dosing interval compliance rates per subject will be determined as follows:

$$\text{Dose compliance rate} = \frac{\text{Number of doses taken within 80\% to 125\% of prescribed dose}}{\text{Total number of doses}} \times 100$$

where the percentage of a prescribed dose is calculated as: (nominal dose taken/prescribed dose) x100

and the ‘nominal dose taken’ will be determined from the nominal potency labeled on the vials used by the subject for each injection of rFIXFc.

$$\text{Dose interval compliance rate} = \frac{\text{Number of doses taken within +/- 36 hours of prescribed day/time}}{\text{Total number of intervals}} \times 100$$

A subject is considered ‘dose compliant’ or ‘dosing interval compliant’ if his respective rate is at least 80%.

Descriptive statistics of the percentage of nominal doses taken per subject within the 80% to 125% range for dosing compliance as well as frequencies for the dose compliance rate (<80%, ≥80%) will be presented for overall prophylaxis regimen for the FAS. Similarly, descriptive statistics of the percentage of doses taken per subject within ±36 hours of the prescribed day as well as frequencies of the dosing interval compliance rate (<80%, ≥80%) will be presented for the FAS.

Based on their per-subject compliance rates for dose and dosing interval (each <80%, ≥80%), subjects will be further classified into the following mutually exclusive categories for overall compliance to their prophylactic treatment as:

- Both dose and interval compliant
- Dose compliant or interval compliant (but not both)
- Neither dose nor interval compliant

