- For subjects on the episodic regimen following the end of a surgical/rehabilitation period, the efficacy period for the episodic regimen starts or restarts (depending on

whether there is a treatment regimen change during the surgical/rehabilitation period) at 00:01 on the day following the end of the surgical/rehabilitation period.

Start and end dates/times for the efficacy period for given treatment regimens and treatment regimen changes will be adjusted for each surgery (major or minor) as necessary.

For subjects on a prophylactic regimen before the start of a surgical/rehabilitation period, the interval of time between the last dose before a surgical/rehabilitation period and the start of the surgical/rehabilitation period will not be attributed to the efficacy period for the prophylactic regimen. By definition, there should not be any treated bleeding episodes in this interval of time.

For subjects on a prophylactic regimen following the end of a surgical/rehabilitation period, bleeding episodes that occur after discharge from a rehabilitation facility but before the next prophylactic dose will be attributed to the surgical/rehabilitation period and hence not counted towards the annualized bleeding rate.

Adjustments Due to Large Injection Intervals

For analysis purposes, the efficacy period will also be adjusted to account for large intervals between injections resulting from missing data. Time between any 2 adjacent rFIXFc injections of greater than 42 days within a prophylactic treatment regimen will be removed from the efficacy period. The efficacy period prior to each such interval will end at the time of the first injection of this interval and restart (or start if it is the first interval of a treatment regimen) at the time of the second injection of this interval. The efficacy period will be adjusted for each identified interval that is not within a surgical/rehabilitation period. Treatment regimens considered for large interval adjustment include individualized prophylaxis, weekly prophylaxis, and personalized prophylaxis regimen with at least 2 routine prophylactic injections (additional injections are not considered due to the sporadic nature of these injections). No adjustment for large injection intervals will be made for episodic treatment regimens.

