6.5.3. Prophylactic Dose (IU/kg) and Dosing Interval (days)

Because prophylactic dosing in study 9HB01EXT is based on variable doses and dosing intervals, the amount of rFIXFc received prophylactically will be summarized as an average weekly dose. Descriptive statistics will be provided using the FAS for each prophylactic regimen.

The average weekly prophylactic dose (IU/kg) and the prophylactic dosing interval will be based on prophylactic doses that are not separated by a bleeding episode. Data to be included in the calculations, specifically the prophylactic doses and the total duration of prophylaxis treatment, will come strictly from intervals representing 2 consecutive prophylactic doses (PR) during the efficacy period (see Section 5.3.2 for a description of the efficacy period). The sum of doses at PR_x and the sum of interval durations (PR_{x+1} minus PR_x) will be determined across all evaluable intervals of PR_x to PR_{x+1}. As such, when a bleeding episode is encountered, the interval stops at the prophylactic dose prior to the event and continues with the first prophylactic dose after the event. The last PR dose during a given treatment regimen will be the end of the last interval used for these calculations. The start and stop time of a treatment regimen and the calculation of total duration in that treatment regimen are described in Section 5.3.1. If a subject is treated in a given treatment regimen more than once during study 9HB01EXT, the sum of doses at PR_x, sum of days in PR intervals, sum of days in PR intervals, and number of PR intervals will be calculated across all durations in that treatment regimen before the average weekly prophylactic dose and dosing interval are calculated using the formula below.

$$\text{Average weekly prophylactic dose} = \frac{\text{Sum of doses at PR}_x}{\text{Sum of days in PR intervals}} \times 7$$

$$\text{Average prophylactic dosing interval} = \frac{\text{Sum of days in PR intervals}}{\text{Number of PR intervals}}$$

For the personalized prophylaxis regimen, additional injections administered will also be included in the average weekly prophylactic dose and average dosing interval calculations.

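### Prophylaxis compliance under SAP 6.5.5.2 can be overstated when missed doses come in runs or are followed by bleeds

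*SAP*

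**What the plan says.** SAP 6.5.5 sets out to measure adherence to the Investigator's dosing recommendations, within the efficacy period. Section 6.5.5.2 defines two per-subject rates.

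- **Dose rate.** "An individual dose will be considered compliant if it is within 80% to 125% of the prescribed dose". The denominator is the doses taken: "All prophylactic injections will be used to determine prophylactic dose compliance".
- **Interval rate.** "The actual dosing intervals will be calculated as the length of time between consecutive prophylactic doses", and the absolute difference between "actual and prescribed dosing intervals must be ≤1.5 day (+/- 36 hours) in order to be compliant".

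The interval rate is restricted to "intervals not separated by a bleeding episode or surgical/rehabilitation period", with 6.5.3 giving the detail: "when a bleeding episode is encountered, the interval stops at the prophylactic dose prior to the event", and counting resumes at the first prophylactic dose afterwards.

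A further restriction comes from SAP 5.3.2: "Time between any 2 adjacent rFIXFc injections of greater than 42 days within a prophylactic treatment regimen will be removed from the efficacy period". That section gives missing data as the reason, but the trigger is the length of the gap alone.

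A subject is compliant on a rate at 80% or more. The top overall category requires both rates to reach 80%.

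**The concern.** Neither rate divides by the number of doses the subject should have taken. The dose rate cannot register a miss at all. The interval rate registers a miss as one overlong interval, with the same weight whether the gap hides one missed dose or five. It then drops two kinds of gap: those over 42 days, and those containing a bleed.

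The second exclusion needs attention. A treated bleed after a lapse still counts in the ABR (SAP 7.1.1), while the lapse before it leaves the compliance table. SAP 5.1.1 itself anticipates FIX activity below 1% in most subjects after 14 days (from 998HB102) or 7 days (from 9HB02PED), so overdue intervals are ones in which bleeding is plausible.

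In an open-label, home-treated study, compliance tables help a reader separate bleeding despite prophylaxis from bleeding after prophylaxis lapsed. If clustered lapses are scored as full compliance, some bleeds may be attributed to the prescribed regimen when no dose had been taken on time.

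**Working it through.** The documents give no compliance result to reproduce. The one stated conversion is right: 36 h / 24 = 1.5 days.

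**Inputs.** Weekly interval 7 days, individualized 8 to 16 days (SAP 3.2.1.2); tolerance 1.5 days, cut 80% (6.5.5.2); removal of gaps over 42 days (5.3.2); bleed-interrupted intervals dropped (6.5.3, 6.5.5.2). The dosing patterns are assumptions. Each dose is taken on schedule at the prescribed amount, so the dose rate is 100% throughout.

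**Formulas.**
- Gap after k consecutive misses = (k + 1) × prescribed interval.
- Interval rate = on-time kept intervals / kept intervals.
- Comparison rate = doses taken / doses scheduled.

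| Weekly pattern | Intervals | Kept | On time | Interval rate | Taken / scheduled |
|---|---|---|---|---|---|
| Every other dose skipped, no bleeds | 52 | 52 | 0 | 0% | 53/105 = 50.5% |
| 5 taken, 1 missed, repeated | 50 | 50 | 40 | 80% | 51/61 = 83.6% |
| 5 taken, 5 missed, repeated | 50 | 50 | 40 | 80% | 51/101 = 50.5% |
| 6 taken, 6 missed, repeated | 48 | 40 | 40 | 100% | 49/97 = 50.5% |
| One 26-week lapse in 52 weeks | 25 | 24 | 24 | 100% | 26/52 = 50.0% |
| 26 regular weeks, then every other dose skipped, no bleeds | 52 | 52 | 26 | 50% | 53/79 = 67.1% |
| The same, with a bleed in every gap | 52 | 26 | 26 | 100% | 53/79 = 67.1% |

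**Isolated misses are caught.** One skipped weekly dose gives a 14-day interval, and 14 − 7 = 7 days exceeds 1.5. Alternate skipping also scores 0% on 3.5-, 8-, 14- and 16-day schedules. With each weekly dose skipped at random with probability one half, an interval is on time with probability 1/2 and kept with probability 1 − (1/2)^6 = 63/64, so the expected rate is about 0.5 / (63/64) = 50.8%. In 20,000 simulated two-year records the mean was 50.8%, the maximum 76.1%, and none reached 80%.

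**Runs count once.** Rows 2 and 3 both score 80%, though row 3 has five times as many misses. Its gap is 6 × 7 = 42 days, which is not over 42 and so is kept.

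**Longer runs vanish.** With six misses the gap is 7 × 7 = 49 days and is removed, so row 4 scores 40/40. Removal starts at 6 consecutive misses on a 7-day schedule (49 days), 5 on an 8-day schedule (48), 3 on a 14-day schedule (56) and 2 on a 16-day schedule (48).

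**Bleeds can move the category.** The last two rows have identical dosing. Only the bleeds raise the rate from 26/52 to 26/26.

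**The case against.** A reader might infer that both rates ignore missed doses, so that anyone who skips half his doses is classed as fully compliant. The documents do not support that. The interval rate is built to detect misses, and scattered half-skipping fails it clearly. Misclassification needs runs of misses or bleeds in the gaps.

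A reader might also infer that the bleed rule always inflates compliance. It does not. It drops every interval containing a bleed, including on-time ones (a bleed on day 3, the next dose on day 7), so its net direction depends on the data. Nor need it change a category. With 52 weekly doses scheduled and five isolated skips each followed by a bleed, 47 doses are taken and there are 46 intervals. The rate is 41/46 = 89.1% with the gaps kept and 41/41 = 100% without, and 47/52 = 90.4% of doses were taken. All are above 80%. If every interval contained a bleed, the rate would be undefined rather than 100%.

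Nor can it be said that ABR becomes uninterpretable. SAP 7.4.2 summarises time from the last prophylactic injection to each spontaneous bleed. Section 7.3.2 reports injections and exposure days over the full regimen duration, ignoring interruptions, so long lapses appear as few injections. All injections are listed. Time removed under the 42-day rule also leaves the ABR denominator.

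These points narrow the concern but do not remove it. Section 7.4.2 omits traumatic bleeds and does not compare the time with the prescribed interval. Section 7.3.2 is not set against prescription. The average dosing interval in 6.5.3 uses the same filtered intervals, so it does not reveal the gaps either.

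Finally, gaps over 42 days may be missing records, as 5.3.2 says, and SAP section 9 describes subjects who could not enter diary data. Counting all such gaps as missed could bias compliance downward. That stands, and it shapes the fix.

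**Conclusion.** The point holds in limited form. The two rates can overstate adherence when misses are clustered or followed by bleeds. The size is conditional: on a weekly schedule, about half the doses can be missed with interval compliance of 80% to 100% and the top overall category, and bleeds in the gaps can move a subject from 50% to 100%. These are illustrations under assumed patterns. The documents do not say how often such patterns occur, so no overall bias can be estimated.

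The consequence is moderate. Prophylaxis compliance is neither a primary nor a secondary endpoint, and it defines no analysis set and no ABR subgroup. All analyses are descriptive. It bears on how on-prophylaxis ABR, a secondary endpoint, is read. The change is worth making because a stated rule can misclassify adherence and the remedy is cheap.

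**What to change.** In SAP 6.5.5.2:

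1. Add a supplementary per-subject rate: prophylactic doses taken divided by doses prescribed, over time on prophylaxis outside surgical/rehabilitation periods.
2. Show it twice, once with gaps over 42 days counted as missed doses and once with them excluded as missing data. Use vial accountability (Protocol 12.1.4) where it can resolve a gap. It may not always do so, since scheduled visits are six-monthly and SAP 6.5.5 draws compliance data from the eCRF and eDiary. In the six-taken, six-missed pattern the two versions give 49/97 = 50.5% and 49/49 = 100%, which shows how much rests on those gaps. In the five-and-five pattern both give 50.5%.
3. Tabulate treated breakthrough bleeds with a known onset time by whether the next prophylactic dose was overdue at onset, meaning later than the prescribed interval plus 36 h after the last prophylactic dose.

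The existing rates can stay. The cost is SAP wording and a little extra derivation from data already collected, and reported compliance will look somewhat lower. The primary endpoint and the ABR calculation do not change.

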6.5.5.3. Compliance of EPD Contemporaneous data entry

Injections must be entered into the EPD in a timely manner. Individual occurrences of injection data entered in the EPD more than 7-day from the date of administration will be reported as protocol deviations. Descriptive statistics of the percentage of subjects with fewer than 80% of their total individual EPD records entered within this 7-day window and those with 80% or greater of records that met these criteria will be presented for overall treatment regimen for the FAS.

The analysis of ABR, duration of dosing, and adverse events in safety, as described in Sections 7.3.1, 7.3.2, and 8.2.1 respectively, will be presented by subgroups based upon this percentage.

7. EFFICACY AND PHARMACOKINETIC ANALYSIS

7.1. General Efficacy Principles

Unless specified otherwise, only data occurring during the efficacy period will be used in analyses and summaries relating to bleeding, consumption, and compliance in the treatment of bleeding episodes; efficacy data collected during the surgical/rehabilitation periods (major and minor) will not be included (see Section 5.3.1).

7.1.1. Bleeding Episodes

Bleeding episodes will be recorded in both the EPD and eCRF; this information will be used to derive the secondary efficacy endpoints. During the course of the study, the Investigator was given the opportunity to disagree with the type of bleed (spontaneous or traumatic), as classified by the subject/caregiver and the subject/caregiver was subsequently given the opportunity to agree or disagree with the reclassification. If the subject/caregiver agreed with the Investigator's assessment, then all analyses subset by type of bleed will be based on the Investigator's determination of the bleed type whether or not the change was made to the subject's records.

A standardized definition of a bleeding episode has been applied to this study, as follows. A bleeding episode starts from the first sign of a bleed and ends no more than 72 hours after the last treatment for the bleed, within which any symptoms of bleeding at the same location, or injections less than or equal to 72 hours apart, are considered the same bleed. Any injection to treat the bleed taken more than 72 hours after the preceding one will be considered the first injection to treat a new bleed. For the purpose of analysis, the latter injection will be associated with a new bleeding episode and classified as type=Unknown. The location(s) associated with the original bleeding episode will be carried forth to the new bleeding episode; the onset date and time of bleeding will be unknown and hence considered missing. Any bleeding at a different location is considered a separate bleeding episode regardless of the time from the last injection.

This algorithm will also apply when a follow-up injection was recorded subsequent to a prophylactic injection. If the follow-up injection was administered >72 hours after the previous injection to treat a bleeding episode (type=spontaneous, traumatic, or follow-up), then the follow-up injection will be classified as a new bleeding episode as described above.

Bleeding at a different location will occur when the general bleeding location is different (e.g., in a joint for the original bleeding episode and subsequently in a muscle) or in a sub-location not initially present if in the same location category (e.g., right elbow for the original bleeding episode and subsequently in the right and left elbows). Conversely, a bleeding episode that originally occurs in the right elbow and left knee and is reported as a new bleed within 72 hours as being only in the right elbow will be considered to be in the same location and hence not counted as a new bleeding episode.

A bleeding episode that occurs in multiple locations will be counted as a single event when determining the overall annualized number of bleeding episodes. However, in summaries by bleeding location, the bleeding episode will be counted in each location for which it is reported with the exception that bleeding that occurs in more than one sub-location of the same location category (e.g., 2 or more different joints) will be counted as just one for that location category.

Only bleeding episodes that were treated with at least one dose of FIX (whether rFIXFc or a non-study drug) will be included in the analysis of endpoints evaluating bleeding. That is, bleeding episodes that were not treated at all will not be included. Bleeding episodes that were treated with non-study medication will be included in the determination of the annualized bleeding rate. The handling of bleeding episodes treated with non-study FIX for other endpoints is discussed in Sections 7.4.1.

Bleeding episodes of an unknown type will be included in the determination of the annualized bleeding rate and in summaries based on bleeding episodes but, unless specified otherwise, will not be included in summary tables where endpoints are summarized by type of bleed.

The per-subject annualized number of bleeding episodes, hereafter referred to as the annualized bleeding rate (ABR), will be calculated for each subject using the following formula:

$$\text{ABR} = \frac{\text{Number of bleeding episodes during the efficacy period}}{\text{Total number of days during the efficacy period}} \times 365.25$$

